When the interview is concluded, participants will receive \$40 in the form of a gift card in Atlanta and Jackson and \$40 in cash in Miami, New Orleans and Baton Rouge. Forty U.S. dollars is a standard amount for OMB-approved qualitative interviews and is not considered a coercive amount for participation. In addition, this amount is consistent with similar studies conducted with a nationwide sample of MSM, accounting for the inconvenience of travel and time. It is also consistent with both CDC and other OMB approved qualitative studies with minors. Respondents will be reminded during consent/assent process that all answers are voluntary, that they may choose to not answer any question and that they will receive the \$40 without regard to their participation in the interview or whether or not they choose to answer any question. Participants who need an HIV test in order to verify HIV negative status will not be compensated for complying with eligibility requirements by getting tested, however, we will direct potential respondents to testing centers where the tests are free.

[Other Interactions](#)

Participants will receive a reminder call, text or email regarding their face-to-face interview appointment⁴. During the initial screening, permission to leave a voice, text and email message will be determined. Permission to leave messages will be checked prior to any reminder calls or messages. Reminder messages will not identify the respondent by name nor the purpose the interview. They will remind the respondent time of the interview and for adults that they should remember to bring the test results if they have them. The type of test will not be included in the message. The interviewer contact information will also be included in the message.

Respondent Burden

The phone screening will take approximately five minutes to complete. We expect to screen approximately 600 callers to enroll 150 respondents. However, the number may need to be higher if, for instance, interested callers are not willing to produce HIV test results.

For the qualitative study, participants will participate in a face-to-face interview lasting approximately one hour depending on the length of participant's responses.

[Benefits to Subject or Future Benefits](#)

The benefits of participating in the study include contributing to new understanding about prevention and protective factors in order to create programs and interventions that may help reduce the high proportion of new cases of HIV among African-American and Hispanic/Latino MSM. Interview respondents will receive a \$40 token of appreciation in the form of a gift card or cash regardless of whether or not they answer any questions during the in-person interview.

[Information Management and analysis software](#)

⁴ Based on C&A agreement TBD.

All data (transcripts without PII) will be kept in encrypted or password protected files or as directed by the CDC TM. Analysis will be done on secured network systems or on stand-alone (non-networked) password protected computers in secured locations as directed by the CDC TM. Analysis software will be N-Vivo 10.1.

Data Management, Monitoring and Statistical Analysis

RSS and Emory will collect data by paper and pencil in face-to-face interviews. Interviews will also be audio-recorded on two devices and transcribed by RSS and Emory on password-protected computers or as directed by the CDC TM. Interviewers will remind respondents not to use PII when responding to questions while being recorded. Recordings will be transcribed exclusive of PII. Descriptors will be used to replace PII mentioned in the transcripts. Access to the encrypted transcript files will require a password and is restricted to staff working on the project. Interviews that were conducted in Spanish will be transcribed directly into English by RSS. Spanish-language interviews are anticipated to take place primarily in Miami. The transcription process for the short response data will include entering those values into an Excel password protected file or encrypted SPSS file as directed by the CDC TM. Encrypted PII-free transcribed data will be transferred to IMPAQ via email, FTP transfer or as the CDC TM directs. IMPAQ will lead security protocol development. Qualitative data (transcriptions without any PII) will be stored on a secure network within the secure areas of IMPAQ's FISMA compliant operation or as directed by the CDC TM. Users are restricted. IMPAQ's information technology security will review all use of the system and take the appropriate corrective actions for improper use.

IMPAQ staff will code data using N-Vivo 10.1 on a secure network or in accordance with the security stipulations of CDC TM. Transcripts will be structurally-coded based on a careful reading of the selected transcripts to systematically identify recurrent pertinent themes and patterns in the data (e.g., perceptions about prevention and prevention behaviors), the IMPAQ lead qualitative analyst will develop a coding structure which will be discussed and further refined in collaboration with the head coder, who will have read the same transcripts. [Attachment 7a.]

After the data have been coded, the next analytic stage involves systematically looking for and examining recurrent thematic patterns in the data to address the main study questions. NVivo10.1 provides powerful tools that can be brought to bear in doing this, to be described shortly, which is one reason why it is so important to have a clear and focused approach that prioritizes the analytic questions of greatest or most pressing relevance. The analytic team is comprised of the RSS PI, [name]; the PI, [name]; and the IMPAQ Lead Analyst, [name], working in conjunction with CDC. The team will discuss and agree to a prioritized list of the topics/questions to be explored analytically, guided by considerations including policy relevance/need; significance in addressing gaps in the literature/ knowledge base; and greatest potential impact of the findings given the qualitative nature of the results. Prioritization can be informed by concrete knowledge of thematic content and richness of the qualitative data set, the timely needs/priorities of DHAP relative to this project; and the available resources. Potentially, each topic can be linked to one or more publications.

Additional statistical analyses will be performed as appropriate for the data set. The majority of the analysis will be done as traditional qualitative analysis.

The principal analytic products for the study, “Understanding Barriers and Facilitators to HIV Prevention, Care and Treatment for Men Who Have Sex with Men (MSM),” will be several articles suitable for publication in peer-reviewed journals. These articles will present the study findings and/or methodology and focus on the topics prioritized by the analytic team, as described earlier. The publication guidelines and authorship process established for the previous task order will be followed in producing the manuscripts. Additionally, a power point presentation describing results and manuscripts that were developed will be produced.

Quality Control/Assurance

Quality assurance is measured by the quality of the respondents, their meeting eligibility requirements and by the quality of the instrument administration. Respondents will be primarily recruited through healthcare and community organizations that serve the minority LGBTQ, MSM and YMSM populations. In addition advertisements, flyers and listservs will also specifically target the population needed. Unless otherwise directed, all adult MSM will need to produce proof of a negative HIV test result obtained at least within the prior six months of the interview date. Thus, the general population of non MSM will have no or little access to recruiting materials. Screener eligibility questions are asked of respondents without alerting them to which criteria make them eligible or ineligible. Those wishing to participate but are deemed ineligible would find it difficult to know which questions affect eligibility (Attachment 2a, 2b). Instruments will be administered by highly skilled interviewers with multiple years of experience in qualitative interview techniques. Quality control will be monitored throughout the project.

Protocols will be in place to monitor the quality of the respondents as well as the quality of the interview, with initial interview transcripts reviewed by the PD or PI of the project. In person training and additional training and communication will be ongoing throughout the field period. Study data will be provided with all appropriate physical and operational security protections to minimize risks to confidentiality. Data will be stored in a physically secure location. Access to identifying data will be restricted to study staff requiring the data to complete their study-related roles. All staff will be trained in confidentiality procedures and sign a statement regarding nondisclosure of participant information.

Additionally, our team will be responsible for protocol adherence including timely data entry. The PI and PD will be responsible for conducting pilot testing of the pre/post and follow up instruments and data collection procedures (e.g., to detect difficulties in understanding questions, etc.) in order to reduce implementation problems during the conduct of the study. All site leaders will be responsible for data management and will oversee security of the data stored on the server.

Coding Analysts will continually re-review, reconcile, and revise any discrepancies to ensure consistency of later coding. IMPAQ will build the electronic codebook during this process. The PI and PD will be updated with identified themes and the relative codes that are created for their review and agreement.

Sample Bias and Study Limitations

We acknowledge that participants who express interest and agree to be in the study may differ qualitatively from those who refuse to participate in the study or refuse to be tested for HIV and therefore may not be broadly representative of our target population.

We have introduced subsample target recruitment goals to ensure that we obtain a balanced quota sample of MSMs representing geographic, racial and ethnic, and age categories. By recruiting in this manner, we will mitigate sampling bias effects. In addition, we recognize the potential for social desirability bias in the conduct of the study. Our interviewers will be trained on effective techniques to ensure that individuals are comfortable and will not be judged on the narrative responses given in the interviews.

PROCEDURES/METHODS HANDLING UNEXPECTED OR ADVERSE EVENTS

Response/Procedures to Reduce Risks of Participation

All interviewers and recruiters will undergo training and evaluation prior to the start of the field period. Interviewers include key staff members such as Project Director [name], Project Manager [name], Principal Investigator [name], and Emory Program Coordinator [name]. In addition, key graduate research assistants from Emory University and other experienced RSS staff members will be trained to conduct in-depth interviews.

For all interviewers, a two-day in-person training will include qualitative interview methods as well as methods for interviewing at risk, social, and economically disadvantaged populations as well as minors. In addition, interviewers will be provided with pre-training study materials. Recruiter training will focus on the consistent administration of the screener, PII protections and protocols, and determining and selecting appropriate participants. All interviewers and recruiters will be active project team members and, at Emory, graduate student assistants.

Prior to the start of the interview, participants will be asked to sign an informed consent or assent form that details the study, including risks and benefits of participation, voluntary nature of participation and the right to withdraw without penalty, time commitment, research contact person, and IRB contact person. Participants will be given the opportunity to ask additional questions they may have before signing the consent to participate. Minors will have the consent read aloud to them. They will retain a copy of the consent for their records.

Inclusion of minors in this study carries a slight risk of mandatory reporting based on the state laws within each state where interviews take place and the professional status of the specific interviewer⁵. Reporting of sexual activity (as defined in each state) would in turn require releasing of private information. In order to minimize any scenario in which a respondent's private information must legally and ethically be released, all respondents are reminded during the consenting process that disclosure of physical harm to self or others or sexual abuse of minors may require mandatory reporting.

To minimize the risks of a confidentiality breach, screening and interviews will be administered in a private area, away from others. RSS and Emory will collect data by paper and pencil and audio recording during face-to-face interviews.

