CDC will work closely with HDs and HIV testing facilities that they fund to encourage cooperation, especially in the process of confirming HIV-negative status and providing space for interviews. Participants will be recruited in the five cities: Miami, FL; New Orleans & Baton Rouge, LA; Jackson, MS; and Atlanta, GA until the target total of 150 participants is

met. Age and socioeconomic status will be tracked to ensure that young (13-30²) and lower SES MSM are well represented in the population as well as minor YMSM (13-17). Advertisements in publications geared towards the LGBTQ community will be used as needed. Individuals who are interested in participating may contact the phone number provided. They will be screened to assess eligibility [Attachment 2a.]. The screening process should take approximately five minutes to complete.

Recruitment Materials

Fliers for the study and advertisement wording will be submitted for approval, and have been attached in this package [Attachment 5c, 5d].

Plans to Monitor Equitable Recruitment

Participant accrual rates will be monitored by the recruitment manager to maintain consistent and accurate procedures. Age and socioeconomic status will be tracked as cases are completed to ensure that young (13-24) and lower SES MSM are well represented in the population as well as YMSM (13-17). We anticipate a sample size of 150 for analysis with targets as detailed on pg. 8. If recruitment falls short we will work with the CDC COR and TM to determine the best course of action, including recruiting additional participants at alternative HIV/AIDS clinics and MSM venues in the city or cities where additional participants are needed or modifying eligibility criteria.

Informed Consent

The informed consent for adults and the informed assent and parental consent waiver for minors application were approved by Emory's IRB. We requested this waiver because it was anticipated that many of the young men and adolescents may be homeless, runaways, or may not be living with parents or guardians. Or, parents may not be aware of their child's sexual orientation or activity. We also recognized that this population is highly vulnerable to domestic violence or other negative consequences if they do disclose their male romantic and/or sexual preferences to family members or caregivers.

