Individuals who are interested in participating will be screened over the phone by either RSS or Emory recruiters. If they are deemed eligible to participate in the face-to-face interview they will be given a detailed explanation of the study, their role in the study, study requirements (including providing proof of HIV negative status for adult MSM), time commitment, and any additional questions they may have will be answered. Eligible participants will be invited to participate in the face-to-face interview. Prior to beginning the face-to-face interview, participants over the age of 18 years will be asked to sign an informed consent form (Attachments 3a, 3b) that has been approved by the Emory IRB. All minors 13-17 years will be required to assent to participation (Attachment 3c, 3d). A waiver of parental/guardian consent was granted by the Emory IRB due to the social risks that young

² Age criteria include targets for 13-24 (50) and 25-44 (60). Of those aged 25-44 we will monitor and attempt to include proportionately more men 25-30.

MSM fear from disclosing their sexual preference to parents/guardians. It is also highly likely that we will encounter young 13-17 year old MSM who are runaways, living on the streets or in shelters, or in safe homes where parental/guardian consent is not feasible to obtain.

We anticipate that the documents presented to prospective participants will include an explanation of the study, risks and benefits of participation, duration of participation, contact person for the research including the chair of the IRB, the voluntary nature of participation, and the right to withdraw without penalty. The form will also detail the types of disclosures that would necessitate an interviewer reporting the disclosure to authorities. Participants may ask any additional questions they may have. If they choose to participate and sign the consent or assent form they will be given a copy of the form for their records. The consent form will be read to respondents uncomfortable or unable to read it themselves. The assent form will be read to all minors.

PROCEDURES/METHODS VARIABLES/INTERVENTIONS

Variables

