⁶ Recruitment logs and transcripts do not contain PII however, they are password protected at all stages of the process as a precautionary measure.

transcripts once they have been through a quality control check and it is confirmed they contain no PII.

IMPAQ will lead security protocol development. IMPAQ's security program is compliant with NIST SP 800-53. Transcriptions, exclusive of PII, will be stored on password protected computers or encrypted flash drives or as directed by CDC TM. IMPAQ staff will code data using a secure network version of N-Vivo 10.1 or as directed by the CDC TM.

Coded data will be analyzed at all three locations, IMPAQ, Emory and RSS. At Emory and RSS, both quantitative and qualitative data will be accessed on password protected PCs either in a password protected network or as directed by the CDC TM. Data will be saved and backed up onto key drives and kept locked up when not in use. No names or identifiers will be used when transcribing or analyzing the data. Names will never be linked with data.

Vulnerable Population Safeguards

Before entry into the research project, potential participants will be screened over the phone or in person by the interviewer. If participants are deemed eligible to participate, the study will be explained in detail including the purpose, the participant's role, study requirements, and time commitments involved and the voluntary nature of their participation. Potential participants will be assured that their care or services will not be affected in any way by their decision of whether or not to participate in the study. They will be given an opportunity to ask questions and receive additional information. They will then be invited to participate in a face-to-face interview. When the participant comes to the face-to-face interview they will be asked to indicate consent on an informed consent or assent form. The consent form includes an explanation of the study, the risks and benefits of participation, the duration and type of participation, description of the procedures, contact person for the study and IRB, the voluntary nature of participation, the right to withdraw without penalty, and an explanation that we ask them not to use names or other PII during the interview. If they agree to participate and indicate by signature or mark on the consent/assent form they will be given a copy of the form for their records.

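### Every assenting minor is handed a copy of a form that explains the study, with no stated option to decline it or have it held, although the protocol warns of violence if family learn of his orientation

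*Protocol*

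**What the plan says.** The rule on copies appears in three places in the protocol.

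- **Informed Consent:** "If they choose to participate and sign the consent or assent form they will be given a copy of the form for their records".
- **Response/Procedures to Reduce Risks of Participation:** "Minors will have the consent read aloud to them. They will retain a copy of the consent for their records".
- **Vulnerable Population Safeguards:** participants who agree and "indicate by signature or mark on the consent/assent form they will be given a copy of the form for their records".

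Informed Consent also lists what the form contains: an account of the study, its risks and benefits, contact persons, the right to withdraw, and the kinds of disclosure that an interviewer would have to report.

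The same section gives the grounds for waiving parental consent. One is that "parents may not be aware of their child's sexual orientation or activity". Another is that the population is "highly vulnerable to domestic violence or other negative consequences if they do disclose" their preferences to family members or caregivers. A third is that many may be homeless, have run away, or live apart from parents or guardians.

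Other materials are guarded. Under Other Interactions, "Reminder messages will not identify the respondent by name nor the purpose the interview". Under Response/Procedures to Reduce Risks of Participation, contact forms collected in project offices omit the project's purpose and the type of respondent.

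**The concern.** The protocol identifies a specific danger to minors, namely family or caregivers learning that a boy is attracted to males. It obtained a waiver on that ground and removed the study purpose from other materials. The sheet of paper that the minor takes away escapes this reasoning. It has to explain the study, and a minor qualifies only by indicating attraction to other males (Case Definition and Exhibit 3). A relative who reads an informative copy could work out why he was eligible.

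What is at stake is participant safety. Emergency Care/Risks to Participation names breach of confidentiality as the primary risk of the study. The protocol describes no scheduled contact after the interview. Handling of Unexpected or Adverse Events deals with security breaches, distress and incidents around the interview, not with later discovery of a form.

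**Working it through.** The protocol gives no figure on this point to reproduce, so the check sets its sections side by side.

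**1. Is the rule conditional?** No. Informed Consent and Vulnerable Population Safeguards both name assent explicitly. In Response/Procedures to Reduce Risks of Participation the rule directly follows a sentence about minors. None of the three mentions declining the copy, leaving it with the study, or an exception by age.

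**2. Does any other section cover the take-away copy?** No. The consent-form safeguards (no Case ID, separate folder) and the rules for locked travel bags and cabinets concern materials in the study's hands.

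**3. What could the copy reveal?** It must explain the study, which concerns HIV prevention in men who have sex with men. It must also set out the reportable disclosures, which Response/Procedures to Reduce Risks of Participation describes as including sexual abuse of minors. The forms themselves (Attachments 3c and 3d) are not shown, and the List of Attachments gives them only the neutral name Pulse. How much the copy tells a parent is therefore a reasonable inference, not an established fact.

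**4. How are comparable items treated?**

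| Item | Study purpose withheld? | Optional for the participant? |
|---|---|---|
| Reminder messages (Other Interactions) | Yes | Yes; permission to leave messages is obtained at screening |
| Office contact forms (Response/Procedures to Reduce Risks of Participation) | Yes | Not applicable; held by the study |
| LGBTQ and mental health provider list (Vulnerable Population Safeguards) | Not stated | Given on request or if the need arises |
| Copy of consent or assent form | No; it must explain the study | No option stated |

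**5. How many minors does it concern?** Exhibit 1 plans 15-20 minors out of 150 participants: 15/150 = 10.0% and 20/150 = 13.3%. All of them fall under the rule. The risk at home applies only to those who live with or return to family or caregivers. The protocol gives no share for this, so the bounds are 0 x 15 = 0 and 1 x 20 = 20 minors. It gives no rate at which such forms are found, so no expected number of harmed minors can be derived.

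**The case against.** The strongest reply is that there is no inconsistency. The waiver stops the study from disclosing to parents by asking their consent, whereas the copy goes privately to the participant, who controls it. Reminders pass through voice, text and email that others may see, and contact forms are study records, so neither is quite like a paper handed over in person. Giving a signer his form is itself a protection, and arguably matters more when no parent consents for him. Nothing stops a minor from discarding it. The form also carries research and IRB contacts, so he could report harm.

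Most of this stands. Giving a copy is not an error, and the sections do not contradict each other. What remains is that the protocol neither tells the minor he may decline nor provides for the study to hold the copy, and it leaves this one item outside precautions it takes elsewhere for the same danger.

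A reader might also infer more than the text supports:

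- **That the copy bears the minor's signature.** The text refers to a copy of the form or of the consent; a blank copy would satisfy it.
- **That each minor is sent home to a household at risk.** The text says only that the copy is for his records, and Informed Consent expects many minors to be homeless, in shelters or living apart from parents.
- **That following the protocol brings about the harm, or that a number of disclosures can be predicted.** Harm needs several further steps: he keeps the form, takes it to a home where his orientation is not known, it is found, and its wording is revealing. The documents quantify none of these.

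**Conclusion.** The point holds as an unaddressed confidentiality risk. Three sections hand every assenting minor a copy of a form that must explain the study and its reportable disclosures, with no stated option to decline it or have it held. The protocol itself says that parents may not know and that disclosure can lead to violence.

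The group concerned is some unknown part of the 15-20 planned minors, between 0 and 20. The conclusion assumes that the assent form, whose wording is not shown, explains the study well enough for a family member to recognise its subject. If the wording is discreet, the risk is smaller.

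This is a cheap improvement in participant safety. It is not a contradiction and has no bearing on the objectives, sample size or analysis.

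**What to change.** In Informed Consent, Response/Procedures to Reduce Risks of Participation, and Vulnerable Population Safeguards, replace the automatic provision with an offer, for example: *Participants will be offered a copy of the form; a minor, or any adult who asks, may decline it or have it held by the study.* Give anyone who declines a card with the research and IRB contacts that mentions neither the study's purpose nor its population. Record the choice, and submit the change to the IRB.

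The cost is a short amendment and a printed card. The downside is that some participants will leave without the written statement of reportable disclosures and withdrawal rights. Reading the assent form aloud, already planned for all minors, together with the held copy and the card, offsets this. A held copy is harder to reach for participants interviewed by travelling staff, so the card should make clear, in neutral terms, that a document can be requested.
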